### List of Abbreviations

Abbreviation	Explanation
AE	Adverse event
ALP	alkaline phosphatase
ALT	alanine aminotransferase
AST	aspartate aminotransferase
AUC 0-28day	Area under the concentration-time curve from time 0 to 28 Days
BMI	Body Mass Index
CI	Confidence interval
CL	Clearance
C max	maximum concentration
CPMS	Clinical pharmacology modeling and simulation
C-SSRS	Columbia suicide severity rating scale
CTCAE	Common terminology criteria for adverse events
C trough	trough concentration
DARS	Data acquisition requirements specification
DMC	Data Monitoring Committee
DMP	data management plan
ECG	Electrocardiogram
eCRF	Electronic case report form
EOS	end of study
GBS	Global Biostatistical Science
GSO-DM	Global study operations-Data management
ITP	Initial Treatment Phase
IP	investigational product
IPD	important protocol deviation
IVRS	Interactive voice response system
kg	Kilogram
m	Meter
MedDRA	Medical dictionary for regulatory activities
mg	Milligram
NCI	National Cancer Institute
OEP	Optional Extension Phase
PD	Pharmacodynamic
PK	Pharmacokinetic(s)

Abbreviation	Explanation
PT	preferred term
Q4W	every 4 weeks
QTc	QT interval corrected
SAE	serious adverse events
SAP	Statistical Analysis Plan
SC	Subcutaneous
SOC	system organ class
TBL	total bilirubin
TFL	Tables, Figures, and Listings
t max	time to maximum concentration
ULN	Upper limit of normal
V c	Central volume of distribution
WHO Drug	World Health Organization Drug

## 1. Introduction

The purpose of this Statistical Analysis Plan (SAP) is to provide details of the statistical analyses that have been outlined within the Protocol Amendment 5 for study 20160172, AMG 334 dated **03 November 2021**. The scope of this plan includes the interim analyses, the primary analysis and the final analysis that are planned and will be executed by the Amgen Global Biostatistical Science (GBS) department unless otherwise specified.

## 2. Objectives, Endpoints and Hypotheses

### 2.1 Objectives and Endpoints

Objectives	Endpoints
Primary	

To evaluate the safety, tolerability, and pharmacokinetic (PK) profile of multiple subcutaneous (SC) doses of AMG 334 in children and adolescent subjects with migraine, respectively

	

Serum PK parameters of AMG 334 (eg, time to maximum concentration [<math>t_{max}</math>], maximum observed concentration [<math>C_{max}</math>], trough concentration [<math>C_{trough}</math>], and area under the concentration time curve [AUC] from 0 to 28 days [<math>AUC_{0-28day}</math>])

Subject incidence of treatment-emergent adverse events (AEs)

Changes in vital signs, 12-lead electrocardiograms (ECGs), clinical laboratory safety tests, and neurological assessments

Key Secondary	

Not applicable

	

Not applicable

Secondary	

Not applicable

	

Not applicable

### Exploratory

## **2.2 Hypotheses and/or Estimations**

Multiple subcutaneous doses of AMG 334 will be safe and well-tolerated, and the PK profiles will support further development of AMG 334 in children and adolescents with migraine, respectively. There will be no formal hypothesis testing; any comparisons made will be descriptive only.

### **3. Study Overview**

#### **3.1 Study Design**

This is a Phase 1b, multicenter, randomized, open-label, multiple-dose study evaluating AMG 334 in male and female children (6 to < 12 years of age) and adolescents (12 to < 18 years of age) with migraine. The study population will consist of 2 cohorts based on body weight at baseline enrolling a total of at least **52** subjects and up to approximately 60 subjects in the study.

Cohort 1 will enroll at least **12** subjects and up to approximately 22 subjects in total with body weight of < 40 kg. At least **9** subjects in Cohort 1 must be aged 6 to < 12 years old including at least **2** subjects aged 6 to < 10 years old, at the time of consent.

Cohort 2 will enroll at least 35 subjects and up to approximately 38 subjects in total with a body weight of  $\geq$  40 kg at baseline. It is anticipated that most subjects in this cohort will be 12 to < 18 years of age. Enrollment requirements for subjects in Cohort 1 and Cohort 2 will be tracked and administered via Interactive Voice Response System (IVRS) to ensure that the minimum number of subjects in each cohort is achieved. Enrollment will be staggered by age category with adolescents (ie, subjects 12 to < 18 years of age) starting enrollment first.

Children 6 to < 12 years of age at the time of consent will participate in the initial treatment phase, for a total of 12 weeks of treatment. Adolescents 12 to < 18 years of age at the time of consent will participate in the initial treatment phase for a total of 12 weeks of treatment after which they will have the option of continuing treatment in an optional 40-week extension phase, for a total of 52 weeks of treatment. A safety follow-up visit will take place 16 weeks after the last dose to complete end of study (EOS) assessments either (i) after completion of the initial 12-week treatment phase, (ii) after completion of the optional 40-week extension phase for those adolescents who choose

---

to continue treatment or (iii) after the last dose received before discontinuation of treatment during the study.

Subjects weighing < 40 kg (Cohort 1) will be randomized in a 1:2 allocation ratio to low dose (35 mg) or high dose (70 mg) for a total of at least **12** and up to approximately **15** subjects completing Week 12 assessments. Subjects weighing  $\geq$  40 kg (Cohort 2) will be randomized in a 1:4 allocation ratio to low dose (70 mg) or high dose (140 mg) for a total of at least 26 and up to approximately 30 subjects completing Week 12 assessments. Treatments will be allocated to qualifying subjects in a randomized order within either cohort through IVRS. Study drug (low-dose or high-dose AMG 334) will be administered in either cohort in an open-label fashion against a background of allowed concomitant medications, including agents for migraine prevention.

[figure not shown]
It is anticipated that at least **52** and up to approximately 60 subjects will be enrolled in the study to ensure that at least **38** and up to approximately **45** subjects complete Week 12 assessments.

During the initial treatment phase, each subject will receive a total of 3 SC doses of AMG 334 administered every 4 weeks (Q4W) on Days 1, 29 ( $\pm$  3 days), and 57 ( $\pm$  3 days), respectively. The study is expected to confirm a PK profile in pediatric subjects that is similar to that in adults, based on population PK analysis, and to provide preliminary safety data in each body weight cohort supportive of the initiation of the AMG 334 Phase 3 studies in the pediatric population. All subjects will be administered AMG 334. Concomitant use of agents for migraine prevention (up to 2 treatments on a stable dose) and for the acute treatment of migraine are permitted during the study. All subjects will be followed for 16 weeks following the last dose of AMG 334.

The overall study design is described in the study schema below:

## Study Design and Treatment Schema

AMG 334 Pediatric, PK / Safety, Open-Label Phase 1 Study Schema  
**N ≈ 60 subjects**

Q4W – Every 4 weeks; SC – Subcutaneous

Cohorts assigned by Day 1 body weight

Children 6 to < 12 years of age at the time of consent, will only participate in the initial treatment phase, for a total of 12 weeks of treatment.

Adolescents 12 to < 18 years of age at time of consent will participate in the initial treatment phase after which they will have the option of continuing treatment in an optional 40-week extension phase.

Subjects completing the initial 12 Week treatment phase and not participating in the optional 40-week extension phase will proceed directly to the Safety Follow-Up Visit.

\* Safety Follow-Up Visit will take place 16 weeks after last dose of IP

### 3.2 Sample Size

The study population will consist of 2 cohorts based on body weight enrolling a total of at least **52** subjects up to approximately 60 subjects in the study. Cohort 1 will enroll at least **12** subjects and up to approximately 22 subjects in total with body weight of < 40 kg at baseline. It is anticipated that most subjects in this cohort will be 6 to < 12 years of age. Cohort 2 will enrol at least 35 subjects and up to approximately 38 subjects with a body weight of  $\geq$  40 kg at baseline. It is anticipated that most subjects in this cohort will be 12 to < 18 years of age.

Subjects weighing < 40 kg (Cohort 1) will receive a dose of 35 mg or 70 mg for a total of at least **12** and up to approximately **15** subjects completing Week 12 assessments.

Subjects weighing  $\geq$  40 kg (Cohort 2) will receive a dose of 70 mg or 140 mg for a total of at least 26 and up to approximately 30 subjects completing Week 12 assessments.

The rate of early discontinuation up to Week 12 assessments is assumed to be 20% and similar across the two cohorts.

All subjects in this study will be administered AMG 334. The sample size for this study is based on clinical and practical considerations to adequately fulfil its objectives and to inform on planned phase 3 pediatric studies. Assuming clearance (CL) and central volume of distribution (Vc) on body weight basis is similar between pediatric subjects and adults, and assuming the percentage coefficient of variation for CL and Vc are 43% and 53%, respectively (based on total between-subject-variability from adult population PK), the proposed sample size provides > 80% power to estimate 95% confidence interval (CI) of CL and Vc within 60-140% of the true parameters for both weight cohorts combined and across the two age categories ([Wang Y et al, 2012](#)).

### 3.3 Adaptive Design

Not applicable.

## 4. Covariates and Subgroups

### 4.1 Planned Covariates

Covariates are not applicable in this study as no formal statistical modeling will be performed.

### 4.2 Subgroups

Selected safety analyses based on age group (6 to < 12 years and 12 to < 18 years) may be performed.

## 5. Definitions

### 5.1 Definition of Terms Included in Study Endpoints

#### Treatment-emergent AE

Events categorized as Adverse Events (AEs) starting on or after first dose of investigational product as determined by “Did event start before first dose of investigational product” equal to “No” or missing on the Events electronic case report form (eCRF) and up to the End of Study date.

#### Treatment-emergent Serious Adverse Events (SAEs)

Treatment-emergent adverse events indicated as serious on the Events eCRF.

#### Device-related Treatment-emergent Adverse Event

A treatment-emergent adverse event with the indicator flag “Is there a reasonable possibility that the event may have been caused by the investigational device” equal to “Yes” on the Events eCRF.

## 5.2 Study Dates

#### Enrollment Date

Enrollment Date is defined as the date collected on the eCRF.

#### Randomization Date

Randomization Date is defined as the date subject was allocated to a treatment group.

#### First Investigational Product (IP) Dose Date

First IP Dose Date is the date on which a subject is administered the first dose of IP following randomization, which may be the same day or after the randomization date, **as recorded on IP Administration eCRF**. For subjects who are randomized but not dosed with IP after randomization, First IP Dose Date is considered missing.

#### First Initial Treatment Phase (ITP) IP Dose Date

**First ITP IP Dose Date is the date on which a subject is administered the first dose of IP in the initial treatment phase, as recorded on IP Administration eCRF.**

#### First Optional Extension Phase (OEP) IP Dose Date

First OEP IP Dose Date is the date on which a subject is administered the first dose of IP in the optional extension phase following completion of initial treatment phase, **as recorded on IP Administration eCRF**.

**Last IP Dose Date**

Last IP Dose Date for each subject is defined as the latest date IP is administered, as recorded on IP Administration eCRF.

**Last ITP IP Dose Date**

Last ITP IP Dose Date for each subject is defined as the latest date IP is administered during the initial treatment phase, as recorded on IP Administration eCRF.

**Last OEP IP Dose Date**

Last OEP IP Dose Date for each subject is defined as the latest date IP is administered during the optional extension phase, as recorded on IP Administration eCRF.

**End of IP Admin Date**

End of IP Admin date for each subject is defined as the date the decision was made to end IP as recorded on the End of IP eCRF.

**End of ITP Date**

End of ITP date for each subject is defined as the date recorded on the End of Initial Treatment Phase eCRF.

**End of OEP Date**

End of OEP date for each subject is defined as the date recorded on the End of Optional Extension Treatment Phase eCRF.

**Subject-level End of Study (EOS) Date**

EOS for each subject is defined as the date the subject last completed a protocol-specified procedure, as recorded on the EOS eCRF page.

**5.3 Study Points of Reference**

**Baseline**

Unless otherwise stated, baseline will be defined as the last assessment taken prior to the first AMG 334 administration (ie, Day 1 pre-dose or Screening if Day 1 pre-dose is not available) of the ITP. For subjects continuing treatment in an OEP after completion of the ITP, their baseline will be the same as the ITP.

For ECG and Neurological Evaluation, the entire set of data from the Day 1 visit will be used as baseline. If the data is missing on Day 1, the entire set of data from the Screening visit will be used as baseline.

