### **2.2.3 Pharmacokinetics**

AMG 334 exhibited nonlinear PK after single-dose SC administrations over the dose range of 1 to 210 mg (Study 20101267). AMG 334 exposure increased more than dose proportionally from 1 to 70 mg and appeared to increase approximately dose proportionally from 70 to 210 mg after a single SC administration of AMG 334. The mean area under serum concentration time curve from time 0 to the last quantifiable time point (AUClast) increased from 171 to 652 µg•day/mL (3.8-fold) and mean Cmax increased from 6.25 to 15.2 µg/mL (2.4-fold) following the 3-fold increase in dose from 70 to 210 mg. Following a 140 mg SC dose maximum serum AMG 334 concentrations (Cmax) were attained at a median time (tmax) of 5.5 days (range 4-21 days). The relative exposure as measured by the area under the concentration time curve (AUC) for SC administration compared with IV administration was approximately 54% for the 140 mg AMG 334 dose. There was no apparent difference in PK parameters between the healthy and migraine subjects. It is expected that AMG 334 administered SC every 4 weeks will be effective in migraine prevention in pediatric subjects. The effective half-life is 28 days.

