#### **6.2.1.1 Dosage, Administration, and Schedule**

A qualified staff member will administer the appropriate dose and number of AMG 334 injections into the abdomen, the upper arm or the upper thigh, the 3 anatomical sites for administration of Investigational Product. For subjects weighing < 40 kg at baseline (Cohort 1), one injection of either 35 mg (0.5 mL) or 70 mg (1 mL) will be administered. For subjects weighing ≥ 40 kg at baseline (Cohort 2) one injection of either 70 mg (1 mL) or 140 mg (1 mL) will be administered.

Subjects in either cohort will be randomly assigned to one of two Investigational Product dose levels; doses are fixed and will not be adjusted for individual subjects during the study. The anatomical sites for administration of Investigational Product are the upper arm, upper thigh, or abdomen.

All subjects in this study will be administered AMG 334 against a background of allowed concomitant medications, including agents for migraine prevention.

AMG 334 will be administered Q4W on Study Day 1, and on Study Days 29 (± 3 days) and 57 (± 3 days). Adolescent subjects will have the option to participate in the optional 40-week extension phase, receiving IP as noted in the Schedule of Activities ([Table 1](#) and [Table 2](#)), at the dose they received during the initial 12 Week treatment phase regardless of any changes in weight that might occur during the study. All subjects will be monitored on site 2 hours post-dose on Day 1 for any acute reactions that might occur. All subjects will be monitored on site for 30 minutes post-dose on Days 29 and 57. The post-dose safety monitoring will be extended for 2 hours if the subject shows any safety concerns post-dose during the last dosing visit. The date, time, injection location, volume (full, partial, or none), and lot number of each treatment will be recorded in the subject's source documents and on the appropriate eCRF. The effects of overdose of AMG 334 are not known. All overdose occurrences must be documented and corresponding adverse events must be recorded on the appropriate eCRF and in the source documents.

The study may be terminated at any point in time at the discretion of the sponsor. Subjects who permanently discontinue IP during the initial 12 week treatment phase will have the EOS/Week 12 visit assessments performed and will then return for the safety follow-up visit 16 weeks after the last dose of Investigational Product. Subjects who

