#### **7.2.16        Initial 12 Week Treatment Phase Visits**

The following procedures will be completed during the 12 week treatment phase at the times designated in the Schedule of Activities ([Table 1](#) and [Table 2](#)). All visits during this phase, except Day 1 are  $\pm$  3 days.

- Body weight pre-dose
- Neurological exam pre-dose
- Vital signs (eg, blood pressure, heart rate, temperature) pre-dose and 30 minutes post-dose; also 2 hours post-dose on Day 1 only.
- Physical examination pre-dose and 30 minutes post-dose.; also 2 hours post-dose on Day 1 only.
- Single 12-Lead ECG pre-dose and 2 hours post-dose on Day 1 only.
- Laboratory Assessments:
  - Chemistry Panel
  - Hematology Panel
  - Urinalysis
  - Urine Pregnancy Test (female subjects of reproductive potential)
  - Drug and Alcohol Screen

- Serious Adverse Event reporting
- Adverse Event reporting

- Modified PedMIDAS pre-dose
- Documentation of concomitant and headache rescue medications.
- Collect blood for biomarker development pre-dose
- Pharmacogenetics (optional) pre-dose

- AMG 334 serum PK collection pre-dose
- Study drug administration (dose will be based on pre-dose body weight collected on Day 1)
- Following the AMG 334 dose administration at Day 1, all subjects will be monitored at the facility for at least 2 hours post-dose, at which point they will be discharged with instructions to return to the research facility according to the procedures provided in the Schedule of Activities ([Table 1](#) and [Table 2](#)). Following the AMG 334 dose administration on Days 29 and 57, all subjects will be monitored at the facility for at least 30 minutes post-dose. The post dose safety monitoring will be extended to 2 hours if the subject showed any safety concerns post-dose during the last dosing visit.

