### **Study Day 1**

Day 1 is defined as the first day that IP is administered to the subject. For subjects who are randomized but not dosed after randomization, the Study Day 1 is defined as the date of randomization. The day before Day 1 is referenced as Day -1.

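### The SAP's ECG and neurological baseline rule omits the pre-dose limit, so read literally it admits post-dose Day 1 data and gives a post-dose baseline when the pre-dose ECG is missing

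*SAP*

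**What the plan says.** SAP 5.3 has two baseline rules. The general one applies unless otherwise stated: "baseline will be defined as the last assessment taken prior to the first AMG 334 administration", which it spells out as "Day 1 pre-dose or Screening if Day 1 pre-dose is not available". The next paragraph states otherwise for two assessments: "For ECG and Neurological Evaluation, the entire set of data from the Day 1 visit will be used as baseline". Its fallback is: "If the data is missing on Day 1, the entire set of data from the Screening visit will be used as baseline". Subjects who enter the extension keep the same baseline.

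SAP 5.3 also fixes what Day 1 is: "Day 1 is defined as the first day that IP is administered to the subject". The Day 1 visit is therefore a dosing visit. Protocol 7.2.16 lists the ECGs as follows: "Single 12-Lead ECG pre-dose and 2 hours post-dose on Day 1 only". Whichever way that line is parsed, Day 1 has a pre-dose and a 2-hour ECG. Protocol 7.2.7 specifies a single ECG at each time point.

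Change in 12-lead ECG and in neurological assessments belongs to a primary endpoint (Protocol 10.1.1, SAP 2.1). The ECG output that the SAP names is a shift in diagnosis from before to after baseline (SAP 9.6.6). For neurology it is the subject incidence of abnormalities (SAP 9.7.3).

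**The concern.** A baseline should precede treatment. The general rule secures this twice, once in the definition and once in the fallback. The ECG and neurological exception secures it in neither place, and because the general rule yields wherever something else is stated, the exception replaces it.

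The stake is the ECG shift table. An abnormality first seen 2 hours after the first dose could be filed as baseline and not appear as a shift. Conversely, if the later normal tracing were taken as baseline, an abnormality present before dosing would look new when it recurred. The 2-hour ECG falls within the acute-reaction monitoring period: "All subjects will be monitored on site 2 hours post-dose on Day 1 for any acute reactions that might occur". Because the baseline carries into the extension, any error also reaches later ECGs, including the end-of-study ECG in Protocol 7.2.18.

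**Working it through.** The plan gives no figure on this point. The check is to apply both rules to the Day 1 schedule and then size one error.

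**Step 1. The two rules, case by case**

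| Day 1 pre-dose ECG | Day 1 post-dose ECG | General rule | ECG exception, read literally |
|---|---|---|---|
| present | present | pre-dose | both; no selection rule |
| missing | present | Screening | post-dose |
| present | missing | pre-dose | pre-dose |
| missing | missing | Screening | Screening |

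The rules part in the first two rows. In the second, Day 1 data exist, so the Screening fallback is not triggered.

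**Step 2. Both ECGs present**

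Write N for normal and A for abnormal, pre-dose first, then 2 hours. The patterns are NN, NA, AN and AA. Compared with a pre-dose baseline:

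- last Day 1 record used: differs for NA and AN, 2 of 4 patterns;
- worst Day 1 record used: differs for NA, 1 of 4;
- pre-dose record used: differs for none, 0 of 4.

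These count patterns, not subjects. They show that the result depends on a derivation that the SAP does not state.

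**Step 3. Does anything restore the pre-dose limit?**

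SAP 5.4.1, 9.1, 9.6.6, 9.7.3 and Section 10 do not. Since there is one ECG per time point, the phrase about the entire set cannot refer to replicate tracings.

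**Step 4. Which post-dose records are in the Day 1 visit?**

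Protocol 7.2.16 gives one post-dose ECG, at 2 hours, and lists the neurological examination as pre-dose. Protocol Table 1 appears to mark a Day 1 ECG at 0.5 hours as well, and a neurological examination at 2 hours. Its columns do not align reliably in the text I worked from, so I treat these marks as probable only.

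**Step 5. Size of one misclassified subject**

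Inputs are from Protocol 10.2 and 5.1: total enrolment 52 to about 60; Cohort 1 from 12 to about 22, randomized 1:2; Cohort 2 from 35 to about 38, randomized 1:4. The change in a percentage is 100/n.

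- All subjects: 100/60 = 1.7 to 100/52 = 1.9 points.
- Cohort 1, 35 mg: if Cohort 2 stops at about 38, a total of 52 needs Cohort 1 of at least 52 − 38 = 14. Then n = 14/3 = 4.7 to 22/3 = 7.3, giving 100/7.3 = 14 to 100/4.7 = 21 points.
- Cohort 2, 140 mg: n = 35 × 4/5 = 28 to 38 × 4/5 = 30.4, giving 100/30.4 = 3.3 to 100/28 = 3.6 points.

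**Step 6. How likely is a drug effect at 2 hours?**

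Protocol 2.2.3 reports a median time to peak of 5.5 days after 140 mg SC, with an earliest value of 4 days. Two hours is 2/(5.5 × 24) = 2/132 = 1.5% of the median and 2/(4 × 24) = 2/96 = 2.1% of the earliest.

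**The case against.** The best defence is that the exception fixes the unit of data rather than its timing: take all items from one visit and do not patch Day 1 findings with Screening findings. The parallel wording for the two visits fits that purpose, and pre-dose may simply have been assumed. SAP 9.6.6 contrasts diagnoses before and after baseline, which sits awkwardly with a post-dose baseline. This is plausible, and if the programmers use the pre-dose record the first row of the table causes no harm. It does not rescue the second row: a subject with only a post-dose Day 1 ECG still has Day 1 data and would not go to Screening.

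It is also fair to say that the harm is narrow. The second row needs a scheduled pre-dose ECG to be missed while a later one is done. The first needs discordant tracings and an unfavourable selection rule. QTc is not summarized, and adverse event tables and the per-subject ECG review do not use this baseline.

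A reader might infer more than the documents support:

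- That the 2-hour ECG would be the only baseline record when the pre-dose ECG is missing. That follows from Protocol 7.2.16, but Table 1 appears to add a 0.5-hour ECG. The supportable statement is that the baseline would be post-dose.
- That the overlap between baseline and the Initial Treatment Phase is a fault specific to ECG. SAP 5.4.1 starts that phase on Study Day 1 by date, so Day 1 pre-dose laboratory, vital-sign and neurological values fall inside it too.
- That one subject could move the 35 mg arm by 25 points. That needs n = 4, hence Cohort 1 at 12. With Cohort 2 at about 38 the total would be about 50, below the minimum of 52.

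**Conclusion.** The point holds as a minor defect in a stated rule. As written, SAP 5.3 admits post-dose data into the ECG baseline, leaves the choice among discordant Day 1 ECGs open, and gives a post-dose baseline when the pre-dose ECG is missing. The last of these is wrong on either reading. The documents do not show that post-dose ECGs will in practice be used for subjects who have both records, because that depends on a derivation not stated.

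The effect is confined to the descriptive ECG diagnosis shift table and, if a post-dose Day 1 examination is in fact scheduled and the summary uses baseline, the neurological abnormality summary. No hypothesis test is involved. The number of subjects affected cannot be estimated from the documents and is probably small. An exposure-driven change at 2 hours is unlikely; an acute reaction or reading variability is possible. The per-subject sizes assume the planned enrolment and allocation, Cohort 2 at no more than about 38, and enrolled counts as denominators. Denominators limited to subjects with both baseline and later ECGs could be smaller and the percentages larger.

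**What to change.** Reword the exception in SAP 5.3 along these lines: *for ECG and neurological evaluation, baseline is the complete set of pre-dose findings recorded at the Day 1 visit; where Day 1 pre-dose findings are missing, baseline is the complete Screening set.* This keeps the no-mixing purpose, if that was the intention. Add a line in 5.3 or 5.4.1 that ECG and neurological data recorded after the first dose on Day 1 are post-baseline.

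Reconcile the Day 1 ECG and neurological time points between Protocol Table 1 and Protocol 7.2.16, so that the records to which the rule applies are clear.

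The cost is one reworded rule, one added line, one derivation flag and a check of the two schedules. No new data are needed.
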